5.2. Secondary Endpoints

Clinical efficacy outcomes:

1. Functional outcome

- a. The proportion of subjects achieve [REDACTED] mRS 0-1 [REDACTED]. The proportion of subjects achieve [REDACTED] mRS 0-2 [REDACTED].
- b. The proportion of subjects with independent functional outcome, defined as mRS ≤ 2 [REDACTED] after the 1st IP.
- c. The proportion of subjects with excellent functional outcome, defined as mRS ≤ 1 [REDACTED] after the 1st IP.
- d. The shift of proportion of subjects with each grade on mRS [REDACTED] [REDACTED] from Baseline.

2. Neurological outcome

- a. The National Institute of Health Stroke Scale (NIHSS) [REDACTED] [REDACTED] after the 1st IP [REDACTED].
- b. The proportion of subjects with neurological outcome improvement, defined as a decrease in NIHSS ≥ 4 points [REDACTED] from Baseline.
- c. The proportion of subjects with neurological outcome improvement, defined as a decrease in NIHSS ≥ 4 points or NIHSS of 0 to 1 point [REDACTED] [REDACTED] from Baseline.
- d. The proportion of subjects with NIHSS ≤ 2 [REDACTED] after the 1st IP.
- e. The proportion of subjects with NIHSS ≤ 1 [REDACTED] after the 1st IP.
- f. Change in NIHSS [REDACTED] from Baseline.

3. The occurrence of recurrent stroke within 90 days after the 1st IP.

4. The change of cognition assessment by Montreal Cognitive Assessment (MoCA) [REDACTED] from Baseline [REDACTED].

Imaging outcomes:

1. The change of infarct volume [REDACTED] from Baseline by magnetic resonance imaging (MRI)/computed tomography perfusion (CTP).
2. The change of hypoperfusion lesion [REDACTED] from Baseline by perfusion-weight imaging MRI/CTP.

This document is confidential.

3. The proportion of subjects with 90% reduction in hypoperfusion lesion [REDACTED] from Baseline by perfusion-weight imaging MRI/CTP.
4. The infarct volume [REDACTED] after the 1st IP by MRI/CTP [REDACTED].

Safety outcomes:

1. The occurrence of symptomatic intracranial hemorrhage (sICH) [REDACTED] after the 1st IP; clinical deterioration defined as an increase in the NIHSS of 4 points or more AND confirmed by MRI/CTP imaging – documentation.
2. The occurrence of asymptomatic intracranial hemorrhage (aICH) [REDACTED] after the 1st IP.
3. The occurrence of mortality due to any reason within 90 days after the 1st IP.
4. The number and severity of AEs within 90 days after the 1st IP.
5. The number of subjects with AEs within 90 days after the 1st IP.

This document is confidential.

6. Analysis Sets

6.1. Enrolled Population

All individuals who sign the ICF. The Enrolled Population will be used for all subject disposition analyses.

6.2. Safety Population

All randomized subjects who receive at least 1 dose of IP. The treatment group assignment in this population will be defined by the treatment actually received. This population will be used for the analysis of safety.

6.3. Intent-to-Treat (ITT) Population

All subjects who are randomized, irrespective of any deviation from the protocol or premature discontinuation. The treatment group assignment will be designated according to initial randomization. The ITT Population will serve as the primary basis for the analysis of efficacy [REDACTED]

6.4. Per-Protocol (PP) Population

All ITT subjects who are treated and complete study procedures through Day 30 without a major protocol deviation potentially impacting efficacy measurement [REDACTED]. The PP population will be used as supportive basis for analysis of efficacy [REDACTED]

6.5. Completers Population

All ITT subjects who are treated and complete study procedures through Day 90 without a major protocol deviation potentially impacting efficacy measurement [REDACTED]. The Completers population will be used as supportive basis for analysis of efficacy [REDACTED]

This document is confidential.

7. Estimands

Estimands approach is not applicable as this is an exploratory trials.

This document is confidential.

8. General Aspects for Statistical Analysis

8.1. General Methods

- Analysis will be carried out using SAS® (version 9.4 or newer, SAS Institute Inc., Cary, NC). Templates for the summary tables, figures and subject data listings will be available separately.
- Data listings will include all data recorded for all enrolled and ITT subjects. Data will further be categorized by treatment group.
- Summary statistics will be presented by treatment group and overall (wherever applicable). For continuous variables, data will be summarized with the number of subjects (n), mean, standard deviation, median, minimum, and maximum by treatment group. For categorical variables, data will be tabulated with the number and proportion of subjects for each category by treatment group.
- This is an exploratory study, i.e., all statistical comparison between the treatment groups is not confirmatory but of descriptive nature. Where appropriate, descriptive statistics may be presented with 95% confidence intervals (CIs).
- The minimum and maximum will be reported with the same degree of precision (i.e., the same number of decimal places) as the recorded data. Measures of location (e.g., mean and median) will be reported to 1 degree of precision more than the recorded data, and measures of spread (e.g., standard deviation) will be reported to 2 degrees of precision more than the recorded data.
- The dictionary (MedDRA and WHO Drug) version used will be specified in corresponding data display footnote.
- Only data from protocol scheduled visits will be included in the summary tables. Data from unscheduled visits will not be included in summary tables but will be included in the listings.
- Any changes to the analyses that are not included in this SAP will be documented in the CSR.

8.2. Key Definitions

- Unless otherwise defined, baseline is defined as the last non-missing assessment prior to the first dosing.
- Study Day 1 is defined as the date on which a subject took the first dose of study drug**. Other study days are defined relative to Study Day 1.

For assessments occurring on Day 1 or after, Study Day will be calculated as (date of assessment – date of first dose + 1). For assessments occurring before Day 1, Study Day will be calculated as (date of assessment – date of first dose).

This document is confidential.

8.3. Missing Data

Missing data will be imputed for the efficacy variables mRS and NIHSS as described in [Section 10.1](#).

Missing or incomplete dates in safety data: In all listings, missing or incomplete dates will be left as they have been recorded. However, for calculation and sorting based on dates and for consideration in summary tables, the following method will be used: The most conservative approach will be systematically considered. For example, if the onset date of an AE/concomitant medication is missing or incomplete, it is assumed to have occurred during the study treatment, except if the partial onset date indicates differently. A missing/incomplete date of medical history or disease diagnosis will be assumed to have occurred before any study treatment.

Missing TEAE relationship will be imputed by 'related' for summary tables.

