## 13.4 Safety Analysis

All safety analyses will be performed using the Safety population. No imputation of missing safety data will be applied.

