10.2.6. Proportion of subjects with 90% reduction in hypoperfusion lesion [REDACTED]
[REDACTED] from Baseline:

The number and percentage of subjects showing 90% reduction in hypoperfusion lesion [REDACTED]
[REDACTED] will be summarized by treatment group. The difference of the
proportions between the treatment groups and the corresponding 95% CIs will be presented.
Comparisons between treatment groups will be made on the observed data using the Chi-square test
[REDACTED].

[REDACTED]

This document is confidential.

11. Safety

Safety analyses will be performed on the Safety population.

Safety will be assessed based on the incidence of AEs and changes in laboratory results, vital signs, and ECG parameters. For repeated safety assessments collected at scheduled time points, the last non-missing pre-dose value will be used as baseline, and the first non-missing value at each post-dose time points will be used in the analyses. However, all pre- and post-dose assessments including repeat assessments will be presented in data listings. Data collected at unscheduled visits will be included in data listings but will not be considered for analyses.

All safety summaries and analyses will be performed using observed data on the Safety population without imputation of any missing safety data.

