11.1. Primary endpoint

Proportion of subjects with AEs, judged to be probably or definitely related to the IP within 90 days after the 1st IP.

The number and percentage of subjects with AEs, judged to be probably or definitely related to the IP within 90 days after the 1st IP will be presented by treatment group on the Safety population. The difference of the proportions between the treatment groups with the corresponding exact 95% Clopper Pearson CIs will be presented.

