11.2.4. Adverse Events

An AE is any symptom, physical sign, syndrome, or disease that either emerges during the study or, if present on or after the 1st IP administration [REDACTED], worsens during the study, regardless of the suspected cause of the event. AEs are defined as Treatment-emergent adverse events (TEAEs) in the SAP and TLFs.

An SAE is any untoward medical occurrence, in the view of either the Investigator or Sponsor, that:

- results in death,
- is life-threatening,
- results in inpatient hospitalization or prolongation of existing hospitalization,
- results in persistent or significant disability/incapacity, and/or
- is a congenital anomaly/birth defect

Other important medical events that may not be immediately life-threatening or result in death or hospitalization, based upon appropriate medical judgment, are considered SAEs if they are thought to jeopardize the subject and/or require medical or surgical intervention to prevent one of the outcomes defining an SAE.

This document is confidential.

Also, Related TEAE is an any event deemed possibly, probably or definitely related to treatment.

All AEs will be coded using the actual version of MedDRA dictionary to provide the system organ class (SOC) and preferred term (PT). Duration of the adverse event (AE) will be calculated and presented in days. Duration of the AE is defined as (AE end date – AE start date) + 1.

The number and percentage of subjects as well as number of events will be presented for TEAE summaries. An overall summary of TEAEs including the following categories will be presented:

- at least one TEAE
- at least one serious TEAE
- at least one related TEAE
- at least one TEAE leading to study drug withdrawal
- at least one TEAE with fatal outcome

A summary table of TEAEs by SOC and PT will be presented. Multiple instances of the TEAE in each SOC and multiple occurrences of the same PT are counted only once per subject. The denominator used for calculating the percentages will be the total number of subjects included in the safety population.

In addition, for each of the following, a summary of TEAEs will be produced at the subject level:

- Serious TEAEs by SOC and PT
- TEAEs by worst intensity by SOC, PT
- TEAEs by maximum relationship by SOC, PT
- TEAEs leading to study drug withdrawal

All AEs for each subject, including multiple occurrences of the same event, will be presented in full in a comprehensive listing sorted by subject number.

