16.2.5. Body of the Data Display

16.2.5.1. *General Conventions*

Data in columns of a table or listing are formatted as follows:

- Alphanumeric values will be left-justified;
- Whole numbers (e.g., counts) will be right-justified; and
- Numbers containing fractional portions will be decimal aligned.

16.2.5.2. *Table Conventions*

- Units will be included where available.
- If the categories of a parameter are ordered, then all categories between the minimum and maximum category are presented in the table, even if n=0 in a given category that is between the minimum and maximum level for that parameter. For example, the frequency distribution for symptom severity would appear as:

Severity Rating	N
mild	3
moderate	8
severe	0

Where percentages are presented in these tables, zero percentages will not be presented and so counts of 0 will be presented as 0 and not as 0 (0%).

- The same convention will be followed for data where categories are not ordered but are pre-specified on the CRF (e.g., Reasons for Discontinuation from the Study, Race, Ethnicity, etc.); thus, all possible responses available on the CRF will be presented in the table even if there are one or more categories with n = 0.
- An Unknown or Missing category will be added to each parameter for which information is not available for 1 or more subjects.
- Unless otherwise specified, the estimated mean and median for a set of values will be printed out to 1 more significant digit than the original values, and standard deviations will be printed out to 2 more significant digits than the original values. The minimum and maximum will report the same significant digits as the original values. For example, systolic blood pressure will be presented as follows:

This document is confidential.

N	XX
Mean	XXX.X
Std Dev	X.XX
Median	XXX.X
Minimum	XXX
Maximum	XXX

- P-values will be output in the format: '0.xxx', where xxx is the value rounded to 3 decimal places. Every p-value less than 0.001 will be presented as <0.001. If the p-value are less than 0.0001, then it will be presented as <0.0001. A p-value returned as >0.999 will be presented as >0.999.

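### Does the SAP's rule of treating a missing adverse-event relationship as related leave the primary safety endpoint undefined?

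*SAP*

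**What the plan says.** Three statements deal with missing safety data.

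- SAP Section 8.3 (Missing Data) gives handling rules for incomplete dates and then adds: "Missing TEAE relationship will be imputed by 'related' for summary tables".
- The introduction to SAP Section 11 (Safety) says: "All safety summaries and analyses will be performed using observed data on the Safety population without imputation of any missing safety data".
- Protocol Section 13.4 says: "No imputation of missing safety data will be applied".

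Two definitions of relatedness are in use.

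- SAP Section 11.2.4, for the general adverse-event tables: "Related TEAE is an any event deemed possibly, probably or definitely related to treatment". This feeds the overall summary row "at least one related TEAE". The same section plans a table of "TEAEs by maximum relationship by SOC, PT".
- SAP Section 11.1, for the primary endpoint: "The number and percentage of subjects with AEs, judged to be probably or definitely related to the IP within 90 days". This uses the top two of the five grades in Protocol Table 4 and leaves out possibly.

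The visible text of SAP Section 11.1 has no separate rule for an event without a causality grade.

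**The concern.** The causality grade of an adverse event is safety data, and a summary table is a safety summary. Section 8.3 and the introduction to Section 11 therefore cover the same record and, read literally, give opposite instructions.

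The imputed value also does not match the primary cut-off. Related spans three grades, of which two meet the endpoint and one does not. A programmer who applied Section 8.3 to the primary table would have to decide what related means there, and two programmers might decide differently. The maximum-relationship table raises a similar question, because related is not one of the five grades.

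At stake would be the numerator of the primary endpoint. If the choice were left until after unblinding, it could be made with the results in view.

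**Working it through.** The plan states no figure on this point, so there is none to reproduce. The check has two parts: a reading of the rules against each other, then a calculation of scale.

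**Which rule governs?**

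1. *SAP against protocol.* The opening of Protocol Section 13 says that the SAP prevails where the two differ. That settles Section 8.3 against Protocol Section 13.4. SAP Section 14 does not try to list departures; it sends any changes to the clinical study report. The absence of an entry there is therefore not an omission.
2. *SAP Section 8.3 against SAP Section 11.* Section 8.3 is the dedicated missing-data section and gives narrow rules for named items. The sentence in Section 11 is a general one, following a paragraph largely about baseline values, repeat assessments and unscheduled visits. The usual reading is that the specific rule is an exception to the general one. The protocol follows the same pattern: Section 13.4 bars imputation, yet the text on other safety analyses in Section 13.4.2 still counts events with a missing onset date as adverse events.

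**What happens to an ungraded event?**

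| Output | If Section 11 governs | If Section 8.3 governs |
|---|---|---|
| Primary endpoint (11.1) | No recorded grade, so not counted | Labelled related, which may mean only possibly; not judged probable or definite, so not counted |
| At least one related event (11.2.4) | Not counted | Counted |
| Maximum relationship (11.2.4) | Default Missing category | No matching grade, so a labelled row or footnote is needed |

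The two rules agree in the first row, the only one that concerns the primary endpoint. In the second row Section 8.3 has a clear and cautious effect, which is presumably its purpose. For the third row, SAP Section 16.2.5.2 supplies a default: "An Unknown or Missing category will be added to each parameter for which information is not available for 1 or more subjects". Section 16 applies its conventions unless the earlier text specifies otherwise.

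**How large could the effect be if an ungraded event were counted?**

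Assumption: 100 treated subjects per arm, from about 200 randomized 1:1. The documents show no expected event rate, so a range of equal counts *x* per arm is used.

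- Shift in one arm's rate per affected subject: 1/100 = 1.0 percentage point.
- Single-arm Clopper-Pearson 95% upper limit: the 0.975 quantile of Beta(*x* + 1, 100 − *x*). For *x* = 0 this is 1 − 0.025^(1/100) = 3.62%.
- Between-arm difference: Newcombe 95% interval, chosen here only for illustration. With *d* the difference, *p* the observed proportions, and *l*, *u* the Wilson limits of each arm, the lower limit is *d* − √[(*p*₁ − *l*₁)² + (*u*₂ − *p*₂)²] and the upper limit is *d* + √[(*u*₁ − *p*₁)² + (*p*₂ − *l*₂)²].
- Example, 1 against 0 events, in percentage points: the Wilson limits are (0.18, 5.45) and (0, 3.70). Lower limit: 1 − √(0.82² + 3.70²) = −2.79. Upper limit: 1 + √(4.45² + 0²) = 5.45.

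| *x* per arm | Difference interval, *x* vs *x* | One subject added to one arm | Single-arm upper limit, *x* to *x* + 1 |
|---|---|---|---|
| 0 | −3.70 to 3.70 | −2.79 to 5.45 | 3.62% to 5.45% |
| 2 | −5.21 to 5.21 | −4.38 to 6.64 | 7.04% to 8.52% |
| 5 | −6.80 to 6.80 | −5.96 to 8.07 | 11.28% to 12.60% |
| 10 | −8.68 to 8.68 | −7.82 to 9.85 | 17.62% to 18.83% |

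In each row the interval contains zero before and after. The upper limit of the difference rises by 1.17 points (*x* = 10) to 1.75 points (*x* = 0).

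**The case for a change.** The strongest case for a change is this. Section 11 says that all safety summaries are covered and that no missing safety data are imputed, and it names no exception. The precedence clause settles SAP against protocol but cannot settle one SAP section against another. Even if Section 8.3 is an exception, its imputed value straddles the primary cut-off, and the primary result is itself a count and percentage that could be called a summary table. The paragraph just before the rule adopts a conservative approach to missing dates, and a programmer might carry that over and count the event. The sponsor thought a missing grade likely enough to write a rule for it, and a clarifying sentence would cost almost nothing.

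Part of this stands. The literal conflict within the SAP is real, and a cross-reference from Section 11 to Section 8.3 would be tidier. The step to a defect in the primary endpoint does not stand. Counting the event would mean replacing the imputed label with a stronger grade that Section 8.3 does not assign, for an endpoint defined by a judgment that was never made. That reading is possible but strained.

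The shells are a separate document, the table index is not visible, and part of the synopsis text on the primary analysis is redacted. Any of these may already state the rule.

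**Conclusion.** No change to the plan is needed. Sections 8.3 and 11 of the SAP conflict in wording, but analysts would resolve this sensibly: treat Section 8.3 as the specific exception, count ungraded events in the related-event row, and base the primary endpoint on recorded judgments. Neither rule, followed as written, gives a wrong primary result.

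The size is at most 1.0 percentage point in an arm's rate per affected subject, assuming 100 treated per arm, and only if an ungraded event were counted against the natural reading. The number of such subjects is not known. It should be small and may be zero, because Protocol Section 12.7.1 requires relationship to be documented for each event, and Protocol Section 14.2 treats an eCRF as complete only once missing data are resolved. SAP Section 8.1 describes all treatment comparisons as descriptive, and no visible decision rule depends on this count.

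The conclusion rests on the visible text and on causality grades being nearly complete at database lock. If many grades were still missing then, the blinded data review before lock would be the natural place to notice it.

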8.4. Visit Windows

Please refer to [Section 4.6](#) for visit windows.

8.5. Subgroups

Efficacy endpoints will be summarized and statistically compared between the treatment groups in the subgroups of the variables used for [REDACTED]. As additional subgroup the [REDACTED] [REDACTED] will be investigated, the comparison will be made for the overall treatment groups. Additionally, where applicable, comparative analyses will be performed with consideration of the [REDACTED]. Such subgroup summaries and analyses will be performed on the ITT population only.

This document is confidential.

9. Subject Disposition, Protocol Deviations, Demographic, Other Baseline Characteristics and Medication

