### 13.3 Efficacy Analysis

#### 13.3.1 Analysis of Secondary Efficacy Endpoints

Analyses of all secondary efficacy and imaging endpoints will be performed on the ITT population as the main analysis and will be repeated on the PP and Completers populations as supportive analysis.

Efficacy endpoints will be summarized and statistically compared between the treatment groups and in the subgroups of the variables used for randomization stratification, also. [REDACTED]

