4.1. Brief Description

This is a multicenter, double-blind, randomized, and placebo-controlled prospective Phase II clinical study, designed to evaluate LT3001 drug product versus placebo in subjects with AIS. The study is planned to take place in multiple countries. Subjects who participate in this trial should be treated with standard of care of AIS therapies when appropriate.

Approximately 200 eligible subjects will be randomized centrally 1:1 to LT3001 drug product or placebo with the stratification factors. Randomization will be stratified according to age [REDACTED], baseline NIHSS [REDACTED], and time of AIS symptoms onset to the 1st IP [REDACTED]

[REDACTED]

[REDACTED]

Each eligible subject will [REDACTED] The first dose of LT3001 drug product or placebo (1st IP) will be administered within 24 hours after stroke symptoms onset. [REDACTED]

[REDACTED]

LT3001 drug product or placebo will be administered [REDACTED].

A Data Safety Monitoring Board (DSMB) will be formed to assess all data (including imaging data) of LT3001 drug product or placebo treatment. [REDACTED] The DSMB will review safety and efficacy data when the thirtieth treated subject has completed study procedures on Day 7 or terminated the study before Day 7. The DSMB will meet after the data presentation and will issue recommendations relating to safety and study conduct. Unscheduled meetings will be recommended and initiated by the Sponsor or the Principal Investigators. [REDACTED]

[REDACTED]

[figure not shown]
[REDACTED]

[REDACTED]

The participation for each subject is approximately 92 days from the Screening (Visit 1) to the last visit.

This document is confidential.

Study Design

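### Testing drug against placebo inside each subgroup does not show whether the effect differs between subgroups, and no interaction analysis is visible

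*SAP*

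**What the plan says.** SAP 8.5 (Subgroups) reads "Efficacy endpoints will be summarized and statistically compared between the treatment groups in the subgroups of the variables used for", and the name of the variables is then blacked out. Protocol 13.3.1 supplies it: arms are to be compared "in the subgroups of the variables used for randomization stratification, also". The protocol synopsis says the same. SAP 4.1 lists three stratification factors: age, baseline NIHSS and time from symptom onset to the first dose. Their cut-points are redacted.

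SAP 8.5 adds one further subgroup, whose name is redacted, which "will be investigated, the comparison will be made for the overall treatment groups". It continues "Additionally, where applicable, comparative analyses will be performed with consideration of the", and the object of that sentence is blacked out. It closes by confining the work to one population: "Such subgroup summaries and analyses will be performed on the ITT population only".

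The visible test for binary mRS and NIHSS endpoints is a Chi-square test at each timepoint (SAP 10.1.1 and 10.1.2). SAP 16.2.4 provides for p-values in efficacy tables. SAP 8.1 and the opening of SAP 10 call all between-arm comparisons descriptive rather than confirmatory. Neither document shows an interaction or heterogeneity analysis, or a rule for reading one subgroup's result against another's.

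**The concern.** A subgroup table is read to learn whether the effect depends on age, severity or delay. A drug-v-placebo test inside one level answers another question: is the effect in this level distinguishable from zero? The answer depends heavily on how many subjects fall in that level. If one level gives p<0.05 and its partner does not, the pair looks like evidence of a differing effect, yet the two estimates may be close together.

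This trial is small enough for that to matter. An evenly split factor leaves about 50 subjects per arm in each level, so a moderate effect that is the same everywhere has roughly a one-in-three chance of reaching significance in any one level. A false impression of who benefits could colour the reading of the efficacy results, which are the trial's secondary objective.

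**Working it through.** The documents give no figure to reproduce: the sample size sections (Protocol 13.1, SAP 4.3) are redacted and the subgroup text contains no numbers.

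**Inputs from the documents.** About 200 subjects randomised 1:1, so 100 per arm (SAP 4.1). Three stratification factors (SAP 4.1). Chi-square test for binary endpoints (SAP 10.1.1). Response rates of 46.67% v 14.29% in the earlier single-dose phase IIa study (Protocol 5.3), used only as an extreme case.

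**Assumptions.** Each factor has two levels, split 50:50 or 70:30. The factors are independent. One binary endpoint is tested at one timepoint, two-sided at 0.05, with no dropout. The true effect is the same in every subgroup.

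**One factor, by formula.** If a and b are the powers in the two levels, the chance that exactly one is significant is a(1−b) + b(1−a).

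- No effect: 2 × 0.05 × 0.95 = 9.5%.
- 55% v 40%, split 50:50. The variance term is 0.55×0.45 + 0.40×0.60 = 0.4875. The standard error in a level is √(0.4875/50) = 0.0987, so z = 0.15/0.0987 = 1.52 and power is 0.33. The result is 2 × 0.33 × 0.67 = 44%.
- 55% v 40%, split 70:30. The standard errors are √(0.4875/70) = 0.0835 and √(0.4875/30) = 0.1275, giving powers of 0.436 and 0.218. The result is 0.436×0.782 + 0.218×0.564 = 46%.
- 46.67% v 14.29%, split 50:50. Power in a level is 0.952, so 2 × 0.952 × 0.048 = 9%.

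**Three factors, by simulation.** The three factors divide the same subjects, so their results are correlated and the single-factor figures cannot simply be multiplied up. Simulation of 20,000 to 40,000 trials per scenario, using the z-test equivalent to Chi-square without continuity correction, gives:

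| Common effect | Split | False contrast, per factor | At least one of three |
|---|---|---|---|
| none (40% v 40%) | 50:50 / 70:30 | 10% / 9% | 21% / 21% |
| 50% v 40% | 50:50 / 70:30 | 29% / 29% | 49% / 48% |
| 55% v 40% | 50:50 / 70:30 | 44% / 46% | 68% / 70% |
| 60% v 40% | 50:50 / 70:30 | 50% / 56% | 75% / 82% |
| 46.67% v 14.29% | 50:50 / 70:30 | 9% / 21% | 18% / 44% |

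**Interaction test on the same data.** A Wald test of the difference between the two risk differences errs in 5-6% of trials per factor and 15-16% for at least one of three, almost regardless of the size of the effect.

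**Precision of the interaction estimate.** At 55% v 40% the overall difference has standard error √(0.4875/100) = 0.070. With equal halves the interaction has standard error √(2 × 0.4875/50) = 0.140, twice as large, so its 95% CI extends about 1.96 × 0.140 = 27 points either side. Power to detect a true 15-point difference between the two levels' effects is about 19% (0.15/0.140 = 1.07, against 1.96).

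**The case against.** The strongest objection is redaction. SAP 8.5 is blacked out in several places, one of them the object of a sentence announcing further comparative analyses. Protocol 13.3.1 is blacked out directly after the sentence cited here, and most of the model text in SAP 10.1 is hidden. A reader might infer that the plan has no interaction analysis. The documents do not support that; one can say only that none is visible. The comparison inside subgroups is nevertheless stated openly in both documents, and a hidden interaction term would not remove its p-values from the tables.

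Second, the false pattern arises only when p-values are read against each other. No visible text prescribes that, and the SAP labels every comparison descriptive. This lowers the stakes. It does not make a p-value inside a subgroup informative about differences between subgroups, and a descriptive aim is better served by estimates with CIs.

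Third, a reader might say that the method usually misleads. That is too strong. For one evenly split factor the chance never exceeds about 50%, and it falls to about 9% with no effect or with a very large one. The figures near 70% need a moderate effect and three factors taken together.

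Two further readings go beyond the text. The documents do not say that subgroup results will decide who enters a later trial. Nor do they say that arms will be compared in every crossed stratum; they refer to subgroups of each variable.

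Finally, the remedy is weak at this sample size. That is true, and it is part of the verdict.

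**Conclusion.** The point stands as a modest one. The plan commits to comparing arms statistically within subgroups of the stratification variables, and nothing visible tests whether the effect differs between those subgroups. P-values inside subgroups can often suggest such a difference when there is none. For moderate common effects (around 15 to 20 points) seen across three factors, they do so more often than not: 68-82% of trials, against 15-16% for interaction tests. With no effect the gap is small (about 21% against 15-16%).

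The sizes rest on assumed two-level, independent factors, assumed splits and event rates, and a single endpoint and timepoint. The extra redacted subgroup and the many endpoints and timepoints would add opportunities for a false contrast. Whether an interaction analysis exists under the redactions cannot be determined. An interaction estimate from about 200 subjects will be imprecise, so a non-significant one would not show that the effect is uniform.

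**What to change.** In SAP 8.5, and to match in Protocol 13.3.1 and the synopsis:

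- Present the treatment difference in each subgroup with its 95% CI, for example in a forest plot, and drop the p-values inside subgroups.
- For each stratification factor, add a treatment-by-factor interaction estimate with 95% CI, unless the redacted text already provides one. For a two-level factor and a binary endpoint this can be the difference between the two subgroup risk differences, so it does not depend on the model terms that are hidden in SAP 10.1.
- State that differences between subgroups are judged only on the interaction estimate, remain exploratory, and that a wide interval or non-significant result is not evidence of a uniform effect.

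The cost is a few sentences of text and a little more analysis work. No new data are needed and trial conduct does not change. The change should be made before unblinding. What is given up is the apparent clarity of a p-value in each subgroup, in exchange for estimates whose imprecision is plain to see.
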